9.1.16.5 Adjudication Committee — Assessment of Abuse Potential of GWP42003-P

A formal Adjudication Committee will be appointed and assigned to this initiative to classify triggered cases. The Adjudication Committee will meet on a periodic basis to review and assess all of the information collected on triggered cases. Only data from patients who have completed the study will be assessed.

A detailed charter will be agreed, which will describe the roles, responsibilities and duties of the members of Adjudication Committee. The Committee will review all of the information collected in the process and in the assessment of the abuse potential of GWP42003-P, such as:

[figure not shown]
- All triggering AE information.
- Supplemental Adverse Event Form (if applicable).
- All triggering drug accountability discrepancies.
- Supplemental Drug Accountability Form (if applicable).
- Site Classification Form.
- Study Medication Use and Behavioral Survey.
- Additional information from site(s) as requested by the Committee.

The Adjudication Committee will assess all of the information. It will form a position on the classification of each event and will write a study-related report, detailing the conclusions and recommendations.

The overall process is summarized in [Figure 9-1](#).

Figure 9-1

**Flow Diagram for Identifying and Evaluating Clinical Trial
Adverse Event Data Through Systematic Categorization
Tabulation and Analysis which can Illuminate an Abuse
Potential Signal**

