4.1.2 Secondary Endpoint(s)

To assess the safety and tolerability of GWP42003-P compared with placebo when taken in combination with CLB. Safety and tolerability will be assessed using the following parameters:

- AEs
- 12-lead Electrocardiogram (ECG)
- Clinical laboratory parameters (clinical chemistry, hematology and urinalysis)
- Vital signs
- Columbia-Suicide Severity Rating Scale (C-SSRS)
- Seizure Frequency
- Abuse Liability

PK parameters (C_{max} , t_{max} , $AUC_{(0-\infty)}$, $AUC_{(0-t)}$, $t_{1/2}$) of the following analytes:

- THC
- THC major metabolites

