9.1.16.1.1 List of 'Triggering Adverse Events of Interest'

During the collection of AEs, if the patient reports an AE consistent with any of the following categories, then the investigator or study coordinator is required to complete an additional Supplemental Adverse Event Form and a Site Classification Form (investigator only) following further discussion of the event(s) with the patient or their caregiver. The categories are:

- Euphoria or inappropriate elation.
- Inappropriate laughter or exhilaration.
- Mood changes.
- Drunk, high or intoxicated.
- Hallucinations (visual or auditory), dissociations, disorientation, agitation.
- Disturbance in cognition, memory, or attention.
- Drug abuse.
- Drug withdrawal or drug withdrawal syndrome.
- Addiction.
- Overdose.
- Misuse of IMP.
- Thoughts of suicide, attempted suicide or suicide.

An AE that is consistent with the above categories will be known as a 'triggering AE of interest' for the purposes of this study.

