9.1.16.4 Study Medication Use and Behavior Survey

This form consists of 18 questions regarding the use of the IMP. The trained investigator or study coordinator will complete this survey as an interview with the patient/caregiver at the final dosing visit (Visit 5 or Visit 12) or withdrawal visit. The answers on the Study Medication Use and Behavior Survey will then be transcribed into the patient's CRF for the study.

The Study Medication Use and Behavior Survey will be completed for all patients in the study and not only those that have reported a triggering AE or drug accountability discrepancy.

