10. WITHDRAWAL

In accordance with the Declaration of Helsinki³¹, the FDA regulations relating to good clinical practice (GCP) and clinical trials^{32,33,34}, the EU Clinical Trials Directive (2001/20/EC)³⁵ and/or other applicable regulations, a patient has the right to withdraw from the study at any time and for any reason without prejudice to his or her future medical care by the physician or at the institution.

The patient must be withdrawn from the study if any of the following apply:

- Administrative decision by the investigator, GW, or a Regulatory Authority.
- Pregnancy.
- Protocol deviation that is considered to potentially compromise the safety of the patient.
- Withdrawal of patient consent.
- Withdrawal of legal representative consent.
- Lost to follow up.
- ALT $>3 \times$ ULN or AST $>3 \times$ ULN **and** (TBL $>2 \times$ ULN **or** INR >1.5).
- ALT or AST $>3 \times$ ULN with the appearance of fatigue, nausea, vomiting, right upper quadrant pain or tenderness, fever, rash, and/or eosinophilia ($>5\%$).
- ALT or AST $>8 \times$ ULN.
- ALT or AST $>5 \times$ ULN for more than two weeks.
- Any other IMP is taken as part of a clinical trial during the study.

Patients may also be withdrawn from the study for any of the following:

- Patient non-compliance.
- AE, which in the opinion of the investigator, would compromise the continued safe participation of the patient in the study.
- Any evidence of drug abuse or diversion.
- Suicidal ideation or behavior of type four or five during the treatment period, as evaluated with the C-SSRS.

Should a patient request or decide to withdraw from the study, all efforts must be made to complete and report the observations as thoroughly as possible up to the date of withdrawal. Patients who withdraw should have their dose of IMP tapered gradually (10% each day) over a period of 10 days, beginning at the time the decision

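### The abuse-potential committee is told to assess only completers, which drops triggered cases in withdrawn patients from its classification and report

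*Protocol*

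**What the plan says.** Section 4.1.2 lists "Abuse Liability" among the safety and tolerability parameters of the secondary endpoint. Section 9.1.16 defines two kinds of trigger: adverse events of interest (Section 9.1.16.1.1) and drug accountability discrepancies (Section 9.1.16.2.1). Each trigger calls for a supplemental form and an investigator's Site Classification Form. Separately, the Study Medication Use and Behavior Survey "will be completed for all patients in the study" (Section 9.1.16.4), at the final dosing visit or the withdrawal visit.

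Section 9.1.16.5 appoints the committee to classify triggered cases. It gives two statements of scope: "Only data from patients who have completed the study will be assessed" and, further down, "The Adjudication Committee will assess all of the information".

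Section 10 lists discretionary reasons for withdrawal under the lead-in "Patients may also be withdrawn from the study for any of the following". They include "Any evidence of drug abuse or diversion" and "Suicidal ideation or behavior of type four or five during the treatment period, as evaluated with the C-SSRS". Section 13.3.1 makes the Safety Set, defined by at least one dose of IMP, the primary analysis set for all safety endpoints.

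**The concern.** The committee exists to judge whether triggered events point to abuse potential. If it sees completers only, a case can leave its review because of the very event it should judge: a patient found to be misusing or diverting the product, or with serious suicidality, may be withdrawn for that reason. Selection would then depend on the outcome. For patients withdrawn because of such an event, the effect runs in one direction only, toward a report with fewer abuse-related cases than occurred. In a trial of 20 patients, one or two missing cases can separate a report that describes a signal from one that describes none.

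**Working it through.** The protocol states no figure for this endpoint, so there is none to reproduce. The check is of the text, followed by an illustration of size.

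**Step 1. Scope of the committee.** Within Section 9.1.16.5, the remit covers all information collected on triggered cases, while the restriction admits completers only. Both cannot hold once a patient with a trigger withdraws. The synopsis (Monitoring of Drug Abuse Liability) repeats the remit without the restriction.

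**Step 2. Data collected against data used.** Sections 9.1.16 and 9.1.16.4 require the survey from every patient, including at a withdrawal visit. Section 9.1.16.5 lists that survey as committee material. For withdrawn patients, the protocol therefore gathers material for a committee that is told not to assess it.

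**Step 3. Analysis set.** Abuse liability is a safety parameter (Section 4.1.2), and Section 13.3.1 assigns safety endpoints to the Safety Set. A completer restriction is narrower, and no reason is given for it.

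**Step 4. Overlap of triggers and withdrawal reasons.**

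| Trigger (Sections 9.1.16.1.1 and 9.1.16.2.1) | Discretionary withdrawal reason (Section 10) |
|---|---|
| Drug abuse, addiction, misuse of IMP, missing bottles | "Any evidence of drug abuse or diversion" |
| "Thoughts of suicide, attempted suicide or suicide" | "Suicidal ideation or behavior of type four or five during the treatment period, as evaluated with the C-SSRS" |
| Intake above target, bottle use beyond expectation | Patient non-compliance |
| Any triggering adverse event | Adverse event compromising safe participation |

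**Step 5. Illustration of size.** Inputs: 20 patients (Section 13.1) and 4:1 allocation (Section 7.2), so 20 × 4/5 = 16 patients on GWP42003-P in the blinded phase. One case is 1/16 = 6.25%. The number of cases and the number withdrawn are assumptions. With x cases of which d are withdrawn, and no other withdrawals, the proportion among completers is (x − d)/(16 − d):

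| Cases x | Withdrawn d | All patients | Completers only |
|---|---|---|---|
| 2 | 0 | 2/16 = 12.5% | 2/16 = 12.5% |
| 2 | 1 | 2/16 = 12.5% | 1/15 = 6.7% |
| 2 | 2 | 2/16 = 12.5% | 0/14 = 0% |

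The same point as a probability: let p be the true case rate per patient and w the share of cases withdrawn, both assumed. The chance that at least one case on GWP42003-P reaches the committee is 1 − (1 − p(1 − w))^16.

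| p | w = 0 | w = 0.5 | w = 0.8 | w = 1 |
|---|---|---|---|---|
| 0.05 | 0.560 | 0.333 | 0.149 | 0 |
| 0.10 | 0.815 | 0.560 | 0.276 | 0 |
| 0.20 | 0.972 | 0.815 | 0.480 | 0 |

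The column w = 0 is what the committee would see if every triggered case were adjudicated.

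**The case against.** **The sentence may be about timing.** It follows directly on the statement that the committee meets periodically, and may only mean that a file is reviewed once it is complete. The survey does not exist until the final dosing or withdrawal visit, which supports this. The reading is possible, but it is not what the text says. The Definition of Terms describes end of treatment as completion or withdrawal, and Section 13.5.1 lists patients completing the study apart from those who stop IMP prematurely. The protocol thus treats completion and early ending as different things. If timing was meant, the change below says so.

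**The data are not lost.** This stands. Adverse events, supplemental forms, the survey and the Site Classification Form, with the investigator's view of relationship and certainty, go into the CRF whether or not the patient later withdraws. A reader might infer that the abuse-liability endpoint as a whole is biased. The documents do not support that, because nowhere do they define the endpoint as the committee's output.

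**Triggers need not lead to withdrawal.** This also stands. Withdrawal for abuse or diversion is discretionary, and triggers such as mood changes or inappropriate laughter are not named withdrawal reasons. A reader might infer that the rule removes every abuse case; it removes those in patients who withdraw.

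**The numbers are hypothetical.** True. The protocol specifies no incidence rate or completer denominator for the committee, and adjudication also covers the open-label extension, where former placebo patients may receive GWP42003-P.

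**The charter or Figure 9-1 may settle it.** Neither can be seen here. The protocol nevertheless fixes the restriction itself, and a charter that followed it would carry the same gap.

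**Conclusion.** The point holds for the committee's classification and report. As written, Section 9.1.16.5 leaves triggered cases in withdrawn patients unadjudicated, and this conflicts with the section's own remit, with the survey at the withdrawal visit and with the Safety Set. Because some withdrawal reasons overlap the triggers, the omission can be related to the outcome, with bias toward no abuse signal.

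The size cannot be fixed from the protocol. It is nil if no triggered case withdraws and complete if all do; the figures above show the range under stated assumptions and do not predict a rate. The conclusion rests on the literal reading of the restriction. It concerns a secondary endpoint and should be corrected, but it does not touch the pharmacokinetic comparison.

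**What to change.** Replace the restricting sentence in Section 9.1.16.5 with: *All triggered cases in the Safety Set will be adjudicated, including those in withdrawn patients, once the patient's participation has ended by completion or withdrawal.* Use the same wording in the committee charter.

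This serves the timing purpose, if that was the intent, and removes the internal conflict. The cost is one sentence and a charter edit. The forms and the survey are already required from withdrawn patients, so no new data collection is needed, and no dosing, withdrawal or other clinical rule changes.

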9.2 Study Procedures by Visit

Patients and their caregivers will be invited to participate in the study and will be issued with the patient information and informed consent or the personal legal representative information and informed consent (refer to [Section 9.1.2](#) and [Section 15.2](#)). Following adequate time to discuss the study with the investigator, nurse, relatives or caregiver, patients/legal representatives who provide written informed consent at Visit 1 will be screened for entry into the study.

9.2.1 Double Blind Phase

9.2.1.1 Visit 1 (Day -14 to -7, Screening)

The following observations will be made at Visit 1: demographics, medical history (including seizure information since diagnosis, history of epilepsy-specific genetic testing and all prior AEDs taken), concomitant medications (including AEDs), physical examination (including height and body weight), ECG, vital signs and AEs.

Clinical laboratory samples (blood and urine) will be taken for hematology, biochemistry, alcohol testing, THC testing, urinalysis and a pregnancy test (using a serum sample, if appropriate). The laboratory results should be available within 3-5 working days after Visit 1. If the results show a patient is ineligible, the patient will not be enrolled into the study. The C-SSRS will be administered.

Patients who satisfy all inclusion and none of the exclusion criteria specified in [Section 6](#) will be assigned a unique patient number and then begin the baseline period. Patients or their caregivers will be given a paper diary to record daily seizure information, rescue medication, concomitant AEDs and AEs; and will be instructed on how to do so. The investigator must record the patient's attendance at the visit and confirm the outcome of screening on the CRF.

9.2.1.2 Visit 2

9.2.1.2.1 Visit 2 (Day 1) – Enrollment (+3 days)

This visit will occur 7–14 days after Visit 1.

The following observations will be made at Visit 2: concomitant medications, (including AEDs), physical examination (including body weight), ECG, vital signs and review of patient diary and AEs.

Clinical laboratory samples (blood and urine) will be taken for hematology, biochemistry, alcohol testing and urinalysis. Blood samples will also be taken for genetic testing if additional consent has been obtained. The C-SSRS will be administered. The investigator must record the patient's attendance at the visit, and confirm the outcome of the visit prior to enrollment.

Following enrollment patients will begin the PK sampling process. Blood samples will be taken for analysis of plasma concentrations of CLB, N-CLB, CBD, CBD major metabolites, THC and THC major metabolites. A baseline PK sample will be taken before the patient takes their morning dose of CLB. Further samples will then be taken at the following times relative to the CLB dose: 15 minutes, 30 minutes, 1 hour, 1.5 hours, 2 hours, 4 hours, 6 hours and 12 hours. Patients will either remain in clinic overnight throughout this PK sampling process or return to the clinic on Day 2 ahead of additional sample collection.

9.2.1.2.2 Visit 2 (Day 2) - Enrollment

This is the second part of the two day enrollment visit. The final PK sample will be collected 24 hours after the Day 1 morning CLB dose.

Following completion of the PK sampling process the following observations will be made on Day 2: concomitant medications (including AEDs), physical examination (including body weight), vital signs and AEs.

GWP42003-P/placebo will be dispensed and both the morning dose of CLB and of GWP42003-P/placebo will be taken in clinic. Patients and/or their caregivers will be provided with individual dosing schedules as described in [Section 8.1.2](#). Each patient will then receive their GWP42003-P/placebo for the 10 day titration period followed by the 21 day maintenance period. Patients, or their caregivers, will be instructed on how to record the diary information.

9.2.1.3 Visit 3 (Day 12 +3 days)

This visit will occur 11 days after Visit 2, Day 1 (enrollment). Patients will return all used and unused GWP42003-P/placebo. The following observations will be made at Visit 3 (Day 12): concomitant medications (including AEDs), physical examination (including body weight), ECG, vital signs, AEs and review of patient diary completion.

Clinical laboratory samples (blood and urine) will be taken for hematology, biochemistry and urinalysis. The C-SSRS will be administered.

9.2.1.4 Visit 4

9.2.1.4.1 Visit 4 (Day 33) (± 3 days)

This visit will occur 32 days after Visit 2, Day 1 (enrollment). Patients will return all used and unused GWP42003-P/placebo. The following observations will be made at Visit 4 (Day 33): concomitant medications (including AEDs), physical examination (including body weight), ECG, vital signs, review of patient diary and AEs.

Clinical laboratory samples (blood and urine) will be taken for hematology, biochemistry, alcohol testing, and urinalysis. The C-SSRS will be administered.

Blood samples will be taken for analysis of plasma concentrations of CLB, N-CLB, CBD, CBD major metabolites, THC and THC major metabolites. A baseline PK sample will be taken before the patient takes their morning dose of CLB, followed immediately by their dose of GWP42003-P/placebo. Further samples will then be taken at the following times relative to the CLB dose: 15 minutes, 30 minutes, 1 hour, 1.5 hours, 2 hours, 4 hours, 6 hours and 12 hours. Patients are expected to remain in clinic throughout this PK sampling.

The investigator must assess adherence to the dosing regimen and recording of rescue medications by reviewing the patient's diary.

9.2.1.4.2 Visit 4 (Day 34)

This is the second part of the two day visit. The final PK sample will be collected 24 hours after the Day 33 morning CLB dose.

Following completion of the PK sampling process the following observations will be made on Day 34: concomitant medications (including AEDs), physical examination (including body weight), vital signs and AEs.

At the end of the blinded phase of the study on Day 34, providing the investigator and patient both agree, patients will be invited to continue taking GWP42003-P and to enter the OLE.

Patients who enter the OLE will be dispensed GWP42003-P on Day 34. At the point of entry to the OLE, patients will be transitioned to the OLE treatment over a 10 day period in order to maintain blinding. The dose may be adjusted up or down by the investigator from the maintenance dose of 20 mg/kg/day in the blinded phase to a maximum of 30 mg/kg/day in the OLE. Patients and/or their caregivers will be provided with individual dosing schedules as described in [Section 8.1.2](#). Patients, or their caregivers, will be instructed how to record the diary information.

Patients who do not enter the OLE will begin a 10 day taper period during which they will taper off their daily dose of GWP42003-P/placebo. The daily dose will be reduced by 10% of the maintenance dose per day and treatment will end on Day 42.

9.2.1.5 Visit 5 (Patients not entering Open Label Extension) (Day 43 +3 days)

This visit will occur 42 days after Visit 2, Day 1 (enrollment) for those patients who do not enter the OLE.

All GWP42003-P/placebo (used and unused) will be collected and a check of the returned GWP42003-P/placebo against usage must be made. A physical examination (including body weight), ECG and vital signs will be assessed and the C-SSRS will be administered. The trained investigator or study coordinator will complete the Study Medication Use and Behavior Survey as an interview with the patient/caregiver. Clinical laboratory samples (blood and urine) will be taken for hematology, biochemistry and urinalysis and a review of concomitant medications (including AEDs) and AEs will be completed. Patient diaries will be collected.

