8.1.2 Dose Escalation and Dose Adjustments

Patients will enter the blinded phase of the study and will be up-titrated over ten days (Day 2 to Day 11) to a maintenance dose or equivalent of GWP42003-P/placebo of 20 mg/kg/day. If GWP42003-P is not tolerated then the dose can be reduced accordingly at the discretion of the investigator. The titration regimen is described in [Table 8.1.2-1](#).

Table 8.1.2-1 Dose Up-Titration Regimen*		
Day - GWP42003-P/Placebo (Blinded Period)	Day - GWP42003-P only (OLE**)	Dose Level (GWP42003-P or equivalent placebo)
2	34	2.5 mg/kg
3	35	2.5 mg/kg
4	36	5.0 mg/kg
5	37	5.0 mg/kg
6	38	7.5 mg/kg
7	39	7.5 mg/kg
8	40	10.0 mg/kg
9	41	10.0 mg/kg
10	42	15.0 mg/kg
11	43	15.0 mg/kg
12 onwards	44 onwards	20.0 mg/kg

*GWP42003-P /placebo is to be taken twice daily. Total daily doses are shown.

** Only patients who were taking placebo during the double-blind period will up-titrate according to this schedule during the OLE period. Those taking GWP42003-P during the double-blind period will down-titrate their blinded IMP whilst simultaneously up-titrating with GWP42003-P, thus maintaining a daily dose of 20 mg/kg/day GWP42003-P throughout.

The titration regimen defined above should be followed to the maximum dose (20 mg/kg/day). Should an AE occur during titration which is attributable to IMP or concomitant AED, then IMP dose should be reduced to the next lower dose. Any other changes in concomitant AED therapy should be reviewed with the medical monitor before being initiated.

For those patients who do not enter the OLE the dose of GWP42003-P/placebo will taper off over 10 days beginning on Day 34. The patient will reduce the dose by 10% of the maintenance dose each day and treatment will end on Day 43.

Patients who enter the OLE period will be transitioned to the OLE treatment over a 10-day period in order to maintain blinding, simultaneously down-titrating blinded GWP42003-P /placebo whilst up-titrating open-label GWP42003-P. As such, patients who were taking GWP42003-P during the blinded period will maintain their 20 mg/kg/day dose throughout the transition from the blinded period into the OLE period and patients who received placebo during the blinded period up-titrate slowly to the 20 mg/kg/day dose in the OLE period. After this has taken place, the

maintenance dose of GWP42003-P may be adjusted up or down at the discretion of the investigator to a maximum of 30 mg/kg/day (no minimum).

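### Visit 5 (End of Taper) is counted from Day 1 and not from the actual start of the taper, so an in-window Visit 5 can collect the study drug up to 2 or 3 days before the last taper dose; the stated last treatment day also differs (Day 42 or Day 43)

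*Protocol*

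**What the plan says.** All references are to the current double-blind protocol (Version 2).

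- **Visit 4.** Section 9.2.1.4.1 gives the target, "This visit will occur 32 days after Visit 2, Day 1 (enrollment"), which is Day 33, with a window of ±3 days. All study drug is returned there. Section 9.2.1.4.2 describes the following day: "This is the second part of the two day visit". On that day, patients not entering the OLE start a 10-day taper.
- **Taper.** Section 8.1.2 has the dose "taper off over 10 days beginning on Day 34", falling by 10% of maintenance per day.
- **End of treatment.** Section 8.1.2 reads "of the maintenance dose each day and treatment will end on Day 43", and Section 4.1 also ends dosing on Day 43. Section 9.2.1.4.2 reads "maintenance dose per day and treatment will end on Day 42", and the synopsis agrees with Day 42.
- **Visit 5.** Section 9.2.1.5: "This visit will occur 42 days after Visit 2, Day 1 (enrollment) for those patients who do not enter the OLE". The heading gives Day 43 with +3 days. At this visit "All GWP42003-P/placebo (used and unused) will be collected", and the physical examination, ECG, vital signs, C-SSRS, laboratory tests and medication-use survey are done.
- **Visit 6.** The synopsis and Section 9.2.1.6 place the safety call four weeks after Visit 5 (or after withdrawal from treatment). Section 4.1 places it four weeks after the end of dosing.
- **For comparison.** Section 9.2.2.8 sets Visit 12, the OLE end-of-taper visit, ten days after Visit 11, where that taper begins. Section 9.2.2 counts the OLE visits from Visit 4.

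**The concern.** The taper and the visit that closes it run on different clocks. The taper follows Visit 4, which has a 6-day span. Visit 5 follows Day 1 and can move only later, by up to 3 days. A site that reads the Visit 5 rule literally after a late Visit 4 would take back the drug while doses of the protocol's own stepwise taper are still scheduled, and would be fully compliant in doing so. The population is patients with epilepsy, so an unplanned shortening of a planned withdrawal matters.

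The clocks also drift apart in the other direction. The End of Taper assessments are meant to describe patients at drug withdrawal, but after an early Visit 4 they can only be made some days later than the nominal schedule intends. The disagreement between Day 42 and Day 43 means that sites cannot tell from the text whether an on-time Visit 5 falls on the last dosing day or on the day after it.

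**Working it through.** **Inputs.** Visit 4 first day: 33 ± 3 (Section 9.2.1.4.1). Taper start: the next day (Section 9.2.1.4.2). Visit 5: 43 to 46 (Section 9.2.1.5). Nominal last dose: Day 42 or Day 43, as stated in different sections.

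**Reproducing the plan's own days.** Visit 4 = 1 + 32 = Day 33. Visit 5 = 1 + 42 = Day 43. Visit 6 = 43 + 28 = Day 71. A taper starting on Day 34 with nine dosing days (90% down to 10%) ends on 34 + 8 = Day 42. With ten dosing days it ends on 34 + 9 = Day 43. Each stated last day therefore has a reading that produces it, but the two readings are not the same.

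**Moving Visit 4 through its window.** Let v be the first day of Visit 4. The taper starts on v + 1. The last dose is on v + 9 (Day 42 reading) or v + 10 (Day 43 reading). The table gives Visit 5 minus last dose, in days, from the first to the last permitted Visit 5 day. A negative value means that drug is collected before the last scheduled dose.

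| Visit 4 first day | Taper start | Last dose, Day 42 reading | Visit 5 minus last dose | Last dose, Day 43 reading | Visit 5 minus last dose |
|---|---|---|---|---|---|
| 30 | 31 | 39 | 4 to 7 | 40 | 3 to 6 |
| 31 | 32 | 40 | 3 to 6 | 41 | 2 to 5 |
| 32 | 33 | 41 | 2 to 5 | 42 | 1 to 4 |
| 33 | 34 | 42 | 1 to 4 | 43 | 0 to 3 |
| 34 | 35 | 43 | 0 to 3 | 44 | −1 to 2 |
| 35 | 36 | 44 | −1 to 2 | 45 | −2 to 1 |
| 36 | 37 | 45 | −2 to 1 | 46 | −3 to 0 |

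**Count over the 7 × 4 = 28 permitted pairs.** Visit 5 precedes the last dose in 1 + 2 = 3 pairs (Day 42 reading) or 1 + 2 + 3 = 6 pairs (Day 43 reading). It falls on the last dosing day in 3 or 4 pairs. On the Day 43 reading, one of those 4 is the fully on-time schedule, Visit 4 on Day 33 and Visit 5 on Day 43.

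**Worst late case.** Visit 4 is on Day 36 and Visit 5 on Day 43. With nine dosing days from Day 37, the scheduled dose is 40% of maintenance on Day 42, 30% on Day 43, 20% on Day 44 and 10% on Day 45. Collection on Day 43 therefore comes 2 days before the last dose, or 3 days before it on the Day 43 reading.

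**Early Visit 4.** The nominal gap from taper start to Visit 5 is 43 − 34 = 9 days. With Visit 4 on Day 30, 31 or 32, keeping that gap would need Visit 5 on Day 40, 41 or 42, all before its window opens. In the most extreme pair (Visit 4 on Day 30, Visit 5 on Day 46) Visit 5 is 7 or 6 days after the last dose. On the Day 42 reading, a Visit 6 counted from that Visit 5 has its target 7 + 28 = 35 days after the last dose, whereas the adverse event definition in Section 12.1.1 puts the safety follow-up visit at 28 days after it.

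**The case against.** A reader might infer that after a late Visit 4 the drug is always collected before the taper can finish. The documents do not support that. Visit 5 may be held as late as Day 46, and for every Visit 4 delay of 1 to 3 days at least one permitted Visit 5 day keeps the nominal 9-day gap. For a Visit 4 on Day 36 that day is Day 46. Early collection is permitted, not forced, and the 2-to-3-day shortfall arises only when the latest Visit 4 is combined with the earliest Visit 5.

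There is more on this side. The visit is named End of Taper. Its window extends only later. Section 4.1 has the taper run until dosing has stopped. For withdrawals, Section 10 treats Visit 5 as the visit that follows a completed taper. No sentence tells a site to shorten the taper. A reader might also see a contradiction between a taper starting on Day 31 after an early Visit 4 and the stated Day 34. The better reading is that Day 34 is the nominal label of the second day of Visit 4. An early Visit 4 removes no taper dose; it only puts the assessments later after the last dose.

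All of this stands, and it limits the size of the point. It does not remove it: the only explicit timing rule for Visit 5 is the count from Day 1, a site that follows it after a late Visit 4 remains in window, and the Day 42/Day 43 disagreement is in the current text whatever the visit windows.

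**Conclusion.** The point holds as a gap in how Visit 5 is anchored, together with a plain contradiction on the end of treatment. Drug may be collected before the last scheduled taper dose in 3 of 28 permitted day pairs (Day 42 reading) or 6 of 28 (Day 43 reading), by at most 2 or 3 days. The End of Taper assessments may fall up to 7 or 6 days after the last dose. These are counts of what the schedule allows, not probabilities of what sites will do.

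The result assumes that the taper start moves with the actual Visit 4. The text supports this: Section 8.1 has the final maintenance dose taken in the clinic at Visit 4, all drug is returned there, and Section 9.1.14 has the next supply dispensed on its second day. If the taper were instead fixed to calendar Day 34, a late Visit 4 would not move its end, but a Visit 4 on Day 34 to 36 would then put the pharmacokinetic sampling day inside the taper, against Sections 4.1 and 8.1.

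Only patients who decline the OLE, out of 20 enrolled, are affected. The pharmacokinetic sampling is complete by the second day of Visit 4, so the primary endpoints are not touched. No view is taken on which taper schedule or last treatment day is right.

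**What to change.** 1. Define Visit 5 relative to the actual second day of Visit 4, as the protocol already does for Visit 12 relative to Visit 11 and for the OLE visits relative to Visit 4. With the nominal 9-day gap, the target would move from Day 40 to Day 46 as Visit 4 moves from Day 30 to Day 36. State whether the +3 days still apply on top; if so, the latest possible day becomes 46 + 3 = Day 49.
2. Reconcile the end of treatment: Day 42 in the synopsis and Section 9.2.1.4.2, Day 43 in Sections 4.1 and 8.1.2.
3. Reconcile the timing of drug collection at Visit 5 with the taper schedule.
4. Reconcile the anchor of Visit 6: four weeks after Visit 5 in the synopsis and Section 9.2.1.6, four weeks after the end of dosing in Section 4.1.

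The cost is wording in the synopsis and in Sections 4.1, 8.1.2, 9.2.1.4.2, 9.2.1.5 and 9.2.1.6, with no added visit. The downside is that the study day of Visit 5 would vary by up to ±3 days with Visit 4.
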